Survey Objective (SO) 1. To measure validated treatment coverage of PZQ and ALB in SAC, and adults relative to coverage targets

SO 2. To compare reported and validated coverage of PZQ and ALB for SAC and adults

SO 3. To assess coverage in SAC and adults disaggregated by gender

SO 4. To assess coverage in SAC disaggregated by school attendance

SO 5. Collect information on why targeted eligible individuals did not receive or accept treatment

- SO 6. To assess the impact of radio campaigns on improving knowledge about schistosomiasis
- SO 7. To assess whether radio campaigns improved attendance/coverage of treatment with PZQ and ALB

Where validated coverage rate is defined as:

Total number of interviewed individuals that ingested the target drug Total number of interviewed individuals * 100 %

Note that people interviewed but with missing information on whether they ingested the drug will be assumed to have **not** taken the drug for the purposes of calculating validated coverage.

Study Design

Overview

The coverage survey will take place in nine implementation units (IUs) known as the district. Each IU will be considered separately. Within each IU, the survey will be household (HH) based in randomly selected villages. See Appendix D for a detailed explanation of the statistical approach to the coverage survey.

Survey team

Interviewers must not have been involved in any previous activities related to the NTD programme, specifically the MDA, to ensure that they remain unbiased.

Selection of enumerators will be done by the Programme Managers, ensuring that none of the interviewers were involved with the MDA in July 2017. The majority of interviewers have experience in coverage surveys, but everyone will attend compulsory training to ensure standardisation of knowledge and ability to carry out coverage surveys. Training will include teaching about schistosomiasis and soil transmitted helminth infections as well as familiarisation with the health questionnaires and the phones that the information will be stored on.

Although programme managers will not take part in any of the individual interviews in interviewee households, they will facilitate in the training and logistics of the survey as well as support the teams of enumerators if problems arise.

See Appendix A for more details of the survey teams and logistics.

Timing of survey

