How frequently do you listen to the radio during a week? READ OPTIONS	 More than once a day At least once a day 2 or 3 times per week Once a week Never
[IF AT LEAST ONCE A WEEK] What radio station do you most commonly listen to? WRITE ANSWER	 Zodiak Station MBC Radio Dzimwe Community Radio Nkhota–Kota Radio Neno Community Radio Mzati Community Radio Dziko Community Radio

English Questions	Participant
	🗖 Mzimba Radio
	Dinosaur Community Radio
	Other
What other radio stations do you listen to?	Zodiak Station
MENTIONED AND STATE OTHERS	MBC Radio
	Dzimwe Community Radio
	Nkhota–Kota Radio
	Neno Community Radio
	Mzati Community Radio
	Dziko Community Radio
	🗖 Mzimba Radio
	Dinosaur Community Radio
	Other
The proceeding questions are played with	
radioclips (10seconds in length) in the	
During June and July 2017, the Ministry of	
Health broadcasted a series of radio shows	
schistosomiasis I will now ask you a few	
questions about these broadcastings.	
During that time, do you recall having listed to	T Yes
this radio clip: [PLAY CLIP 1: Mother	
testimonial]?	
[IF YES] Can you tell us what you recall was	A Mother describes a conversation with a doctor
TICK ALL ELEMENTS RESPONDENT IDENTIFIES	Malawi's children have SCH
AS PART OF CLIP	SCH affect mental and physical health
	SCH may show no symptoms
	Children need treatment (medicine) every year
	Distribution is for free
	Children who don't attend school can receive treatment
	Children need to eat prior to MDA.
During that time, do you recall having listed to	The second secon
this radio clip: [PLAY CLIP 2: Doctor testimonial]?	□ No
[IF YES] Can you tell us what you recall was mentioned in this radio clip?	A doctor talks to the audience about SCH
TICK ALL ELEMENTS RESPONDENT IDENTIFIES	Malawi's children have SCH
AS PART OF CLIP	SCH affect mental and physical health
	SCH may show no symptoms

English Questions	Participant
	Children need treatment (medicine) every year
	Distribution is for free
	Children who don't attend school can receive treatment
	Children need to eat prior to MDA.
During that time, do you recall having listed to	T Yes
this radio clip: [PLAY CLIP 3: Give me my broakfast]?	□ No
IF RECALLED FITHER CLIP 1, 2 OR 31 Did you	
discuss the content of any of those clips with	Yes
your family, friends or neighbours?	L No
[IF YES] What topics did you discuss with them?	MDA dates
TICK ALL TOPICS MENTIONED	Malawi's children have SCH
	SCH affect mental and physical health
	SCH may show no symptoms

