	Children need treatment (medicine) every year
	Distribution is for free
	Children who don't attend school can receive treatment
	Children need to eat prior to MDA.
	Other (specify)
Apart from the clips we played to you, did you	T Yes
lune and July 2017 about MDAs against [LOCA]	□ No
TERM FOR SCH]?	
[IF YES] What information was provided in these	MDA dates
radio programmes?	Malawi's children have SCH
	SCH affect mental and physical health
	SCH may show no symptoms
	Children need treatment (medicine) every year
	Distribution is for free
	Children who don't attend school can receive treatment
	Children need to eat prior to MDA.
	Uther (specify)

Individual Answer Code

Answer codes for Household an	d Individual questions
23a: What is your occupation?	24b: What type of school do you attend?
1. Farmer	1. Primary (public or private)
2. Merchant	2. Secondary (public or private)
3. Health worker	3. Religious school
4. Housewife	
5. Student	
6. Fisherman	
7. Medicines distributor	
8. Teacher	
9. Village Head	
10. Does not work	
11. Other (please specify)	
25a. How did you hear about the drug	27b: Reasons for not swallowing PZQ
distribution?	28b: Reasons for not swallowing ALB/MEB
1. Teacher	1. Too young
2. Village Meeting	2. Too old
3. Posters / flyers	3. Pregnant
4. Health professional	4. Breast feeding
5. Newspaper	5. Too sick
6. Radio	6. Feels healthy
7. TV	7. Fear of side effects
8. Town crier (loud speaker)	8. Bad smell or taste
9. Place of worship	9. Tablets are too large
10. Banner	10. Rumours
11. Other (please specify)	11. Does not know
	12. Drugs ran out
	13. Was at work
	14. Not living in the village at time of MDA
	15. Absent from school on day of MDA
	16. Does not attend school
	17. There was no MDA
	18. Had not heard about MDA
	19. Too far from distribution point
	20. Refused to answer
	21. Was not invited to MDA
	22. Had not eaten before MDA
	23. Too many tablets
	24. Medicine does not work
	25. Other (please specify)

27d: Where did you take PZQ?	29: How did you take the PZQ and ALB tablets?
28d: Where did you take ALB?	1. All at the same time
1. School	2. I took them all throughout the day but not all at
2. Home (door-to-door)	the same time
3. House of the village head	3. I took them all but not on the same day
4. Central point in the village	4. One tablet a day until they were all finished
5. Local Health Centre	5. I took some but not all of them
6. District Clinic	6. I was given the tablets but did not swallow them
7. Other	7. Do not remember

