8. Does not know	
32: Who decided whether you took the	e 33: Did you know beforehand when and where the
treatment or not?	MDA would take place?
1. Me	1. Did not know when or where
2. Father	2. Knew when only
3. Mother	3. Knew where only
4. Other family member	4. Knew when and where
5. School teacher	
6. Village Head	
7. Traditional Healer	
8. Health worker or drug distributor	
9. Other (please specify)	
10. Did not know about the distribution	
34: How far was the distribution point	
from your home if walking?	-
1.0 - at home or in school	
2. Less than 30 minutes	
3. 30 to 60 minutes	
4. 1 to 2 hours	
5. More than 2 hours	
6. Do not know	

Translated Survey

English	Chichewa
Village Questions	
What is the total population of the village?	Kodi muli ndi anthu ochuluka bwanji mmudzi muno
What is the number of households in the village (interviewee to estimate if not known)	Muli mabanja angati mmudzi muno
Source of population data?	Munagwilitsa njira yanji kuti mupeze chiwerengero chimenechi
When was the mass treatment for schistosomiasis carried out?	Mankhwala a Likodzo anagawidwa liti mmudzi muno
Where was the mass treatment provided in the village?	Kodi mankhwalawa amagawidwa kuti
Did this treatment include adults? (should be swapped with question 15)	Kodi aakulu amalandila nawo
If the treatment was community based, how was treatment in the village carried out?	Ngati anaperekedwa kumudzi, ndi njira yanji anasata
Household Questions	
Does your household have mobile telephone?	Muli ndi foni ya mmanja
Does your household have a television?	Muli ndi kanema/TV
Does your household have electricity ?	Kodi nyumbayi ili ndi magetsi
Does your household have a radio?	Muli ndi wayilesi
Does your household have a telephone(landline)?	Kodi muli ndi foni ya chingwe/mnyumba
Does your household have a refrigerator?	Muli ndi filiji
Does any member of your household own a bicycle?	Alipo amene ali ndi njinga ya kapalasa mnyumba muno
Does any member of your household own a motorcycle or motor scooter?	Alipo amene ali ndi njinga ya moto nyumba muno
Does any member of your household own a car or truck?	Alipo amene ali ndi galimoto yaying'ono kapena lore mnyumba muno

English	Chichewa
Does any member of this household have a bank account?	Alipo amene ali ndi bukhu la ku banki mnyumba muno
What is the main source of drinking water for members of your household?	Mumatunga kuti madzi akumwa

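### Two background radio items that bear on SO 7 misclassify some respondents as printed: the listening scale has two gaps and an overlap, and item 25a has no code for people who did not hear of the treatment round

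*Protocol*

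**What the plan says.** The objective is SO 7 (Protocol, Study Objectives): "To assess whether radio campaigns improved attendance/coverage of treatment with PZQ and ALB".

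The Individual Questionnaire in Appendix C collects several radio-related items. Two matter here.

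- **Listening frequency.** The question is "How frequently do you listen to the radio during a week", in the present tense. Appendix B tells interviewers in general not to read answer options aloud, but this item is marked as an exception. The five options are, in order: more than daily, "At least once a day", "2 or 3 times per week", weekly, and never. The next item, on the main station, is put only to people who listen weekly or more often.
- **Source of information (item 25a).** The code list headed "How did you hear about the drug" distribution has 11 codes. Radio is code 6 and the last is an other category with a written answer. The form asks the interviewer to enter a code, in the singular.

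Elsewhere the same code lists allow for people who were unaware. Among the reasons for not swallowing the tablets (27b/28b) is "18. Had not heard about MDA", and among the answers on who decided (32) is "10. Did not know about the distribution".

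**The concern.** An answer scale should give every respondent exactly one correct place, and the listening scale does not. The options are read aloud, so a respondent who falls in a gap has to choose a wrong answer, and the analyst cannot later tell who did so.

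Item 25a has a similar fault. A person who never heard of the round has no code, so the interviewer must use the other category, leave the item blank, or enter a source that does not apply. If only one source is entered, a person told by both radio and a teacher may be recorded under teacher alone. The Protocol says school-age children were treated mainly in schools and that radio ran alongside other social mobilisation, so hearing from more than one source is likely.

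What is at stake is the supporting evidence for SO 7. Clip recall is prompted: the interviewer says that the Ministry broadcast the material, plays a clip and asks whether it is remembered. General listening and source of information are collected before that prompt, so they are a natural check on over-reported recall. That check is weaker if they are miscoded.

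**Working it through.** The plan states no figure on this point, so the check compares the printed options with possible answers.

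**Step 1: the listening scale.** Input: the five options in Appendix C. For each weekly frequency, count the options that are literally true.

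| Times per week | Options that fit |
|---|---|
| 0 | 1 (never) |
| more than 0, under 1 | 0 |
| 1 | 1 (weekly) |
| 2 or 3 | 1 |
| 4, 5 or 6 | 0 |
| 7 (once daily) | 1 |
| more than 7 (e.g. 14, 21) | 2 |

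The scale therefore has two gaps and one overlap.

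**Step 2: where the misplaced respondents go.**

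- The 4–6 group must choose the daily option or "2 or 3 times per week". Either answer keeps them among people who listen at least weekly, so they still get the main-station question.
- The under-weekly group must choose weekly (an overstatement) or never (an understatement). Those pushed to never are not asked their main station. The printed condition on that question would exclude them even with a correct code, so a new code also needs a decision about the condition.
- The more-than-daily group can take the first option read out, so the overlap does less harm than the gaps.

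**Step 3: item 25a against the rest of the form.**

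| Item | Records unawareness? | Asked of |
|---|---|---|
| 25a, how heard | No code; only free text under other | No skip printed |
| 27b/28b, code 18 | Yes | Only people who did not swallow that drug |
| 32, code 10 | Yes | No skip printed |
| 33, code 1 | In part: date and place not known in advance | No skip printed |

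The form expects unaware people but gives them no code in 25a. They are partly identifiable from the other three items.

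**Step 4: one source or several.** The radio-content items tell interviewers to tick everything mentioned. Item 25a asks for a code. That points to a single source but does not state it.

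**Step 5: what else measures exposure.** Yes/no recall is asked for each of three clips and referred to June–July 2017, giving a 0–3 count. The elements recalled are ticked for clips 1 and 2. Other June–July broadcasts, and their content, are recorded. Household radio ownership (E4), home language and station items also precede the clips.

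**The case against.** The strongest reply is that SO 7 does not depend on these two items. The Protocol never names either as its exposure variable, and that choice may properly sit in an analysis plan that is not at hand. The clip items are dated and graded. This stands. A reader might infer that exposure cannot be graded at all, and Step 5 shows that it can. Nor are these two the only measures taken before the clips, since radio ownership, language and stations come earlier as well, although none of those gives frequency or source.

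A reader might also infer that unaware people are lost to the survey. They are not: three other items catch many of them, and the free text in 25a could hold the answer. Any misclassification is confined to 25a.

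Single coding of 25a is an inference. The same code-entry instruction follows the plural question on reasons for not swallowing, and the programmed phone form is not shown. This objection also stands, so the under-counting of radio is possible and not established.

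It is tempting to claim a known pull towards no effect. With two equal groups and a symmetric error rate m, the observed difference is the true one times (1 − 2m). That model does not fit. The scale errors mostly move people between neighbouring levels, and any 25a error goes one way. The 25a error could also be related to the outcome: the 2012 survey found school attenders about 4–6 times more likely to receive both drugs, and they are the children most likely to be coded under teacher.

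Finally, the frequency item asks about current listening at an October interview, while the clips began on 25 June. Habitual listening is a defensible background measure, and asking about June–July would add recall error. This is a trade-off, and the point does not rest on it.

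**Conclusion.** The point holds as a minor defect in supporting measures. It is certain from the printed form that the listening scale has no place for 4–6 times a week or for less than weekly, that its top two options overlap, and that 25a has no code for not having heard. It is probable, but only inferred from the format, that 25a takes one source and so may under-count radio among people who also heard another way.

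The documents give no distribution of listening, no share of unaware people and no misclassification rate. Neither the size nor the direction of any bias in the radio–coverage association can be derived. Campaign-specific exposure can still be graded from the prompted clip items, and unawareness is partly recoverable. SO 7 is not defeated, and the coverage estimates under the other objectives do not use these two items.

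**What to change.** - **Listening frequency:** replace the five options with seven that are exclusive and exhaustive: more than once a day; once a day; 4–6 times a week; 2–3 times a week; once a week; less often than weekly; never. Decide whether the less-than-weekly group should also get the main-station question, and print the condition to match.
- **Item 25a:** instruct interviewers to tick every source mentioned, and add a code for not having heard about the MDA.
- **Use:** take both items beside clip recall when SO 7 is analysed, as measures collected before the prompt.

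The cost is small: edits to options and codes on the phone and paper forms before training, slightly longer lists, and possibly less comparability with any earlier use of these items.

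If the form cannot be changed, splitting the scale at weekly or more removes the effect of the overlap and of the 4–6 gap, because both neighbouring answers fall on the same side. It does not resolve the under-weekly gap. Item 25a could then be read with items 27b/28b, 32 and 33 to flag unaware respondents.

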Figure 2: Results from previous coverage survey in 2014. Chikwawa, Rumphi and Salima were selected to be revisited during the 2016 coverage survey.

2016

The 2016 coverage survey was conducted in six districts. One district in each region was purposively selected (Chikwawa, Rumphi and Salima), as these were previously surveyed during the 2014 coverage survey and results had demonstrated a need for improvement. In addition, three other districts randomly selected, one from each of the same three region were also surveyed Mchinji, Karonga and Neno districts.

Overall, the surveyed coverage was above the WHO recommended coverage of 75% of SAC in 5 of 6 districts surveyed. When adjusting for population size Mchinji fell below the 75% coverage for SAC. Reported coverage was not significantly different from surveyed coverage in four of the districts for ALB and PZQ, reported coverage was significantly different than surveyed coverage in the remaining two remaining districts, one higher and one lower than reported.

This survey also found there was a significant difference in the coverage between those who do and do not attend school for all districts and there was no significant difference in coverage between the genders. The full protocol and recommendations report can be found here:

https://share.imperial.ac.uk/fom/IDE/SCI/The%20Hub/MWI_2016CoverageSurveyProtocol_EN.docx

https://share.imperial.ac.uk/fom/IDE/SCI/The%20Hub/MWI_Coverage_Recommendations_Report_ EN.docx

Details of the MDA in Malawi 2017

The MDA took place between the 10-14th July 2017. The MDA was conducted in every district in Malawi except the islands of Likoma. SAC were targeted in every district and treatment predominantly delivered in schools for the SAC, as well community-based treatments for children who do not attend school and adults in the high-risk areas.

In addition to the standard radio campaigns and social mobilisation that are conducted annually, the MoH was supported by SCI and Development Media International (DMI) with the delivery of an enhanced media plan which involved 3×1 minute radio clips which started with the Doctor testimonial (25/6/17 - 1/7/17), followed by the Mother testimonial (2/7/17 - 8/7/17) and lastly the clip "Give me my breakfast" Appendix F. Each of the clips was broadcast 70 times (7 times adjacent to the News), across 9 radio stations and in 4 languages: Chichewa, Lhomwe, Tumbuka and Yao.

Coverage targets for MDA in 2017

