	(Enter one number)	
11	How many adult males live in this house (15 or	
	(Enter one number)	
12	How many adult females live in this house (15 or	
	older)?	
	(Enter one number)	
13	How many boys live in this house (5-14 years	
	old)?	
1/	(Enter one number)	
14	(Enter one number)	
15	Notes about household interview	
	Answered by interviewer	
Equ	ity Questionnaire — To be answered by the househ	old head or other adult interviewee
E1. (Does your household have mobile telephone?] Yes
(Tick	one box)	
E2. [Does your household have a television?	
(Tick	one box)	
		_ No

E3. Does your household have electricity ?	The Yes
	□ No
E4. Does your household have a radio?	T Yes
	□ No
E5. Does your household have a telephone(landline)?	The Yes
(Tick one box)	□ No
E6. Does your household have a refrigerator?	The Yes
	□ No
E7. Does any member of your household own a	T Yes
bicycle? (Tick one box)	
E8. Does any member of your household own a	The Yes
motorcycle or motor scooter? (Tick one box)	D No
E9. Does any member of your household own a car	T Yes
or truck? (Tick one box)	D No
E10. Does any member of this household have a bank	T Yes
E11. What is the main source of drinking water for	Piped into dwelling
(Tick one box)	Piped into yard/plot
	Public tap / standpipe
	Tube well or borehole
	Unprotected dug well
	Unprotected Spring
	Surface water-river, lake, dam, pond
	Other
E12. What kind of toilet facility do members of your	Flush or pour flush toilet
(Tick one box)	Ventilated Pit Latrine (VIP) latrine
	Pit latrine without slab / open pit
	Pit latrine with slab
	□ No facility/bush/field
	Other
E13. Do you share this toilet facility with other	Yes
E14. What type of fuel does your household mainly	Electricity
(Tick one box)	Wood
	Charcoal

	□ Other
E15. What is the main material of the floor in your	Cement
household?	Ceramic Tile
	Earth, Sand, Dung
	☐ Other
E16. What is the main material of the exterior walls	Stone walls with lime/cement
In your household? (Tick one hox)	Unburnt bricks
	Cane/pal/trunks/dirt
	Bamboo/tree trunks with mud
	Cement Cement
	Burnt bricks
	☐ Other
E17. What is the main material of the roof in your	Thatch/palm leaf
household? (Tick one hox)	Pal/Bamboo/grass
	🗖 Iron Sheet
	□ Other

Individual Questionnaire

English Questions	Participant
Name of person randomly selected? (Enter name)	
Was this person interviewed?	☐ Yes
(Tick one box)	□ No
If person not interviewed:	Absent during survey
Reason for no interview?	Refused to participate

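### SO6 cannot be answered with the Appendix C form because no schistosomiasis knowledge item reaches people who report no radio exposure; SO7 supports only an association

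*Protocol*

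**What the plan says.** The Study Objectives section of the protocol lists two radio objectives: "SO 6. To assess the impact of radio campaigns on improving knowledge about schistosomiasis" and "SO 7. To assess whether radio campaigns improved attendance/coverage of treatment with PZQ and ALB".

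The section on the 2017 MDA describes the campaign: three one-minute clips, starting on 25 June 2017, before the MDA of 10–14 July. On intensity it says: "Each of the clips was broadcast 70 times (7 times adjacent to the News), across 9 radio stations and in 4 languages".

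Appendix C, Individual Questionnaire, carries the measurement. The radio section plays extracts of 10 seconds and asks about recall of each, for example "this radio clip: [PLAY CLIP 2: Doctor testimonial". A yes for clip 1 or clip 2 leads to "IF YES] Can you tell us what you recall was mentioned in this radio clip", with eight elements for the interviewer to tick. Clip 3 has the recall item but no content item. The Translated Survey follows the same order and the same conditions.

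The Household Questionnaire also records radio ownership: "E4. Does your household have a radio".

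**The concern.** To speak of a campaign's effect on knowledge, the survey needs the same knowledge outcome in people who were reached and people who were not. The form asks about message content only after the respondent has claimed exposure. For clips 1 and 2 it does so directly after part of the message has been played. The form would then yield a description of what self-declared listeners can repeat, under an objective that promises an effect on knowledge. This cannot be repaired after fieldwork.

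For SO7 the stake is smaller. The data allow a comparison, but the word *improved* claims more than a comparison of self-reported listeners with non-listeners can show.

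**Working it through.** The protocol states no figure for SO6 or SO7, so there is nothing to reproduce. The check is of questionnaire routing: which items depend on reported exposure.

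**Items with schistosomiasis content (Appendix C, Individual Questionnaire)**

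| Item | Who is asked |
|---|---|
| Content of clip 1 (mother) | Only those who recall clip 1 |
| Content of clip 2 (doctor) | Only those who recall clip 2 |
| Content of clip 3 (breakfast) | No such item |
| Topics discussed with others | Only those who recall a clip and discussed it |
| Content of other broadcasts | Only those who heard another broadcast |

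**Items asked regardless of radio exposure**

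| Item | What it measures |
|---|---|
| Recognition of the props | Awareness of the MDA |
| Knowing in advance when and where the MDA was held | Awareness of the MDA |
| How the person heard of the MDA | Source of information |
| Swallowed PZQ; swallowed ALB | Coverage (the SO7 outcome) |
| Listening frequency, including never | Exposure |
| Recall of clips 1, 2 and 3 | Exposure |

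Someone who recalls no clip and heard no other broadcast meets no item from the first table. The second table contains no item on knowledge of the disease.

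**Consequence for SO6.** Let K be the share of exposed people who know a given message and U the share among people who report no exposure. The quantity of interest is K − U. K is observed, though partly prompted. U is not observed and can be anything from 0 to 1. So:

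K − 1 ≤ K − U ≤ K

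| K (illustrative) | Lower bound | Upper bound |
|---|---|---|
| 0.3 | −0.70 | +0.30 |
| 0.5 | −0.50 | +0.50 |
| 0.7 | −0.30 | +0.70 |

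The interval has width K − (K − 1) = 1 and contains zero for every K from 0 to 1. More interviews sharpen K and leave the bounds as wide.

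**Prompting among the exposed.** Appendix B (Interviewing selected individuals) tells interviewers not to supply information that they will later ask for. Playing an extract and then asking for its content sits badly with that rule. The size of the problem is unknown: the extract is 10 seconds of a one-minute clip, and the protocol does not say which of the eight elements it contains.

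**SO7.** Outcome and exposure are both in the second table, so coverage in recallers can be set against coverage in non-recallers. What limits it is design:
- exposure is self-reported in October for broadcasts in June and July, and is asked after the swallowing questions;
- schooling predicts treatment strongly. The 2012 survey found attending children about 4–6 times more likely to be treated, and the 2016 survey found a significant difference in every district surveyed. If radio exposure also follows schooling or household assets (an assumption), the contrast is confounded.

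**The case against.** The strongest case on the other side has four parts.

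*The aim is coverage.* The stated study aim is to monitor treatment coverage, SO6 and SO7 are the last of seven objectives, and the sample size is not built on them. This stands: SO1 to SO5 are untouched. It does not make SO6 answerable.

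*The analysis plan may deal with it.* This stands for the choice of model and covariates, whose absence is not counted here. It fails for the SO6 outcome, which no analysis can supply if nobody was asked.

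*Not all content questions depend on recalling a clip.* Correct: the item on other broadcasts does not. Those respondents are exposed too, so the gap among the unexposed remains.

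*There are earlier data.* Four of the listed districts (Salima, Karonga, Mchinji, Rumphi) had a coverage survey in 2016, and a knowledge survey was done before and after the 2014 MDA in six districts, including Dedza, Salima and Rumphi. A reader might infer that SO7 lacks any pre-campaign measure; for coverage that would be wrong. These data have no control group and the protocol does not tie them to SO6 or SO7. For SO6 they do not help, because the 2017 form has no general knowledge item to set against 2014.

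A reader might also infer that SO7 has no unexposed group. The form contradicts this: people who recall no clip or never listen are asked about swallowing both drugs. Nor do the documents establish that the clips reached the whole country. They give stations and languages, while the form records home languages outside those four.

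**Conclusion.** For SO6 the concern holds. With this form the number of knowledge observations in people who report no exposure is zero, and the effect on knowledge is bounded only by an interval of width 1 that includes zero. This rests on the printed routing of Appendix C and on no assumption about recall or knowledge rates; the K values above only illustrate it.

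For SO7 only a narrower point holds: a comparison is possible, but it is observational with self-reported exposure, so the causal wording goes beyond the design. It is tempting to put a figure on the bias by assuming that treated people recall the clips more often than untreated people. The documents give no recall rates, so no figure is offered.

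**What to change.** 1. In Appendix C, before any clip is played, ask every interviewee one unprompted question on what they know about schistosomiasis and its treatment. Tick the answers on the content list already in the form, without reading it out. Then play the clips and ask about recall. Make the same change in the Translated Survey.
2. Reword SO6 as the association between reported radio exposure and knowledge about schistosomiasis.
3. Reword SO7 as the association between reported radio exposure and coverage with PZQ and ALB, replacing *improved*. With clip recall as the exposure, adjust for items already collected, such as radio ownership, listening frequency, household assets and school attendance. Details can sit in the analysis plan.

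The cost is one extra question per interview, its translation, a re-ordering on the phone and paper forms, and a weaker claim for two objectives. If the question is not added, SO6 should be limited to describing what people who report exposure recall of the messages.
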